## 7.4 CONCOMITANT MEDICATIONS, TREATMENTS AND PROCEDURES

All concomitant prescription medications taken during study participation will be recorded on the case report forms (CRFs). For this protocol, a prescription medication is defined as a medication that can be prescribed only by a properly authorized/licensed clinician. Medications to be reported in the CRF are concomitant prescription medications, over-thecounter medications and non-prescription medications.

## 7.5 PROHIBITED MEDICATIONS, TREATMENTS AND PROCEDURES

The medications and substances listed below are prohibited for the specified time periods:

- **Buprenorphine**, either as part of a maintenance program or any illicit/non prescribed is prohibited for the duration of the study.
- Methadone is prohibited at least 14 days prior to Day 0 and for the duration of the Study.
- All other **opioids** are prohibited for the duration of the study unless approved by the PI or study clinician (see section 7.7)
- **Oral naltrexone** is prohibited for at least 30 days prior to Day 0 and for the duration of the study
- Other forms of extended release naltrexone (e.g. Vivitrol) is prohibited for at least 24 months prior to Day 0 and for the duration of the study

## 7.6 PROPHYLACTIC MEDICATIONS, TREATMENTS AND PROCEDURES

#### 7.6.1 Prophylactic Medications

One dose of IV antibiotic within 30 minutes of the surgical procedure is given as part of the implantation procedure (7.1.1.3):

2g cefazolin IV If allergic to cephalosporins or penicillin, then alternative is 600 mg clindamycin

#### 7.6.2 Management of Infection/Inflammatory Responses to the Wound/Implant Site

All Participants will have their wound site / implant site regularly assessed as per 7.1.1.4 for signs of infection and/or inflammatory reactions. Particular attention shall be paid during follow-up visits at day 4, 8, 14 and 21 (as per 7.3.11) for signs of infection to the wound site or early signs of an inflammatory reaction to the implant. Symptoms and signs relating to redness, excessive itchiness and/or increasing pain at the implant or wound site may be attributed to the inflammatory response. Symptoms relating to edema, spreading cellulitis, fever and general feeling of malaise are likely to be attributed to infection of the implant or wound site. Inflammatory reactions tend to occur much more frequently than infections. Treatment for inflammatory reactions or infections should be performed as specified below.

#### Infection treatment protocol

Infections present in participants as spreading cellulitis with other clinical indicators such as fever or general malaise. Spreading cellulitis involves redness of the skin which may extend several centimetres around the wound and extend over the area of the implant. Participants

with spreading cellulitis should be treated immediately with antibiotics (e.g., cephalexin) with physical exam and/or laboratory results used to monitor treatment response. If the infection does not resolve with oral antibiotics, a course of IV antibiotics may be necessary.

#### Inflammatory responses without an infection

Signs of redness, swelling, tenderness, itchiness or pain as identified from the ISEF after day 14 without the presence of fever or general feeling of malaise, suggests the onset of a mild inflammatory response to the implant only and the treatment regime described below (level 1 to level 4) should be implemented.

#### Level 1 treatment (25 mg prednisone)

Participants should be prescribed prednisone at 25 mg daily for the first 7 days followed by a tapered dose of 12.5 mg for an additional 14-days. The participant should be evaluated 3 days after the start of prednisone. If symptoms have not improved after 3 days then participants shall progress to Level 2 treatment.

#### Level 2 treatment (50 mg prednisone)

If Level 1 treatment is not resolving the pain and swelling, the dose of prednisone shall be increased to 50 mg per day. The participant should be re-assessed after 3 days. If after 3 days symptoms are improving, then the participant should return to the Level 1 treatment protocol. If after 3 days the symptoms have not improved, then participant shall progress to Level 3 treatment protocol.

#### Level 3 treatment (betamethasone and fluid assessment)

Participants who have failed to respond to Level 2 treatment, shall stop their oral prednisone and be given an injection of betamethasone, with 1 mL diluted in saline or local anesthetic (1% lidocaine, 3mL) injected around the implant site where inflammation is occurring in the absence of fluid build-up.

If there is fluid present prior to the betamethasone injection, the fluid must be aspirated. To achieve aspiration of the fluid, a needle with a wide bore is required to aspirate what can be quite thick viscous pus-like fluid. The aim of the drainage is to a) relieve tension and b) remove the fluid build-up. It is therefore important to lavage the fluid space until a CLEAR ASPIRATE is obtained. Lavage the space with normal saline or Hartman's solution. This normally requires multiple lavages, usually about 10mL each time. The final drainage(s) is/are performed without suction, to avoid dislodging/damaging the implant. Drainage and lavage are followed with a brief course of oral prophylactic antibiotic.

Where there are two implant sites, a second injection will be required for the second site (if it is also affected by the inflammatory process). The participants should rest for 30 min following the procedure to maximize the chance of the betamethasone remaining in place.

Note: betamethasone should not be substituted for any other steroidal injection with an alcohol base carrier as this will affect the implant composition.

After 3 days of review, if inflammatory symptoms have fully resolved and there are no signs of an infection then no further treatment is required and participant is observed only. If inflammatory symptoms have improved significantly but not fully resolved then participant should return to Level 1 treatment protocols. If inflammatory symptoms have slightly improved but not fully resolved a second round of betamethasone injections can be commenced.

#### Level 4 treatment (removal of implants)

In participants that do not respond adequately to the treatment regime, the implant(s) should be surgically removed. This can be achieved by a surgical incision over the implant site and should be done by the study surgeon when possible.

#### Inflammatory response with secondary infection

Some participants will develop fluid around their implant as an inflammatory response to the implant. The build-up of fluid causes pressure and symptoms such as pain which can result in the fluid tracking through the line of least resistance and be expelled through the initial surgical incision. This can lead to the wound opening and the risk of secondary infection, as well as implant expulsion. If the implant and wound site is treated according to level 1 to level 4 protocols for inflammatory responses then the risk of this occurring is reduced.

Where the fluid build-up is great enough to cause rupture and discharge, the open wound is at risk of secondary infections. This clinical situation is actually primarily due to an inflammatory response to the implant with a secondary outcome of an infection as a result of an open wound. In such cases, the inflammatory response should be treated as per the inflammatory response protocol starting at level 3 with the addition of oral antibiotics. Treatment with appropriate oral antibiotics should be initiated on the diagnosis and modified if necessary based upon results of culture swabs from the surface of the wound.

Most of the wounds close within a few days of the treatment resulting in the process settling as the fluid drainage no longer keeps the wound open. If the infection is not resolving after 3 days of oral antibiotics, then IV antibiotics should be introduced. In participants that do not respond adequately to the treatment regime, the implant(s) should be surgically removed. This can be achieved by a surgical incision over the implant site and should be done by the study surgeon when possible. Antibiotics shall be continued after surgical removal to treat the remaining infection until all symptoms have resolved.

#### 7.7 RESCUE MEDICATIONS, TREATMENTS AND PROCEDURES

As naltrexone acts as an opioid blocker participants requiring pain relief during the study period will be offered appropriate pain medications e.g. tramadol, reginal blocks or partial opioid agonist such as buprenorphine.

## 7.8 PARTICIPANT ACCESS TO STUDY AGENT AT STUDY CLOSURE

N/A

## 7.9 REIMBURSEMENT COSTS

Participants will receive reimbursement as follows.

- \$50 for each of the two screening visit (2 visits)
- \$50 for the consent visit (1 visit)
- \$400 for Day -1 to Day 2, the Admission Days (either 1 or 2 visits)
- \$50 for each scheduled outpatient visit (25 visits). Participants will receive an additional incremental bonus of \$10 for each subsequent visit attended (Visit 1: \$50, visit 2: \$50+\$10, Visit 3: \$50+\$20, Visit 4: \$50 +\$30 ...). In case the scheduled visit is missed the value of the bonus is reset to the starting value of \$10. This schedule is designed to reinforce adherence to all study safety assessments. Participants will not be penalized for missed visits during the COVID-19 pandemic as long as they attend telephone/video visits in place of the scheduled clinic visit.
- Travel reimbursements in addition to the amounts specified above, participants will receive \$20 for travel at each visit, and up to \$50 in travel if participants provide receipts.

The total amount of reimbursement should a participant attend every scheduled visit is \$4,800 plus a maximum of \$1500 in travel reimbursements depending on provided receipts.

If a participant is required to return for further PK or AE follow-up visits, then they will receive \$50 plus the incremental bonus, plus \$20 for travel, or up to \$50 in travel if participants provide receipts.

## 8 ASSESSMENT OF SAFETY

#### 8.1 SPECIFICATION OF SAFETY PARAMETERS

Safety will be assessed on the basis of:

- the incidence of death
- the incidence of SAEs
- the incidence AEs leading to discontinuation
- the incidence common AEs
- the incidence complications of insertion
- the incidence implantation site reactions
- laboratory abnormalities indicating hepatic problems (absolute values and changes over time)

#### 8.1.1 Definition of Adverse Events (AE)

AEs will be identified from the telephone interviews, face to face visits or from the CRF. They will be recorded on an AE form.

#### Definitions

An AE is any untoward medical occurrence in a clinical investigational participant administered a pharmaceutical product and which does not necessarily have a causal relationship with this treatment. An AE can therefore be any unfavorable or unintended sign (including an abnormal laboratory finding), symptom, or disease temporally associated with the use of a medicinal investigational product, whether or not considered related to the medicinal product. An adverse event is any adverse change (developing or worsening) from the patient's pre-treatment condition, including concurrent illness.

The investigator must make the distinction between exacerbation of pre-existing illness and lack of therapeutic efficacy.

## 8.1.2 Definition of Serious Adverse Events (SAE)

A SAE is any adverse experience occurring during the study period that:

- results in death;
- is life-threatening;
- results in inpatient hospitalization or prolongation of existing hospitalization;
- results in a persistent or significant disability/incapacity; or
- results in congenital anomaly/birth defect.

A *life-threatening* AE is one that actually places the participant at immediate risk of death. A participant's reaction is not classified as life-threatening simply because more severe manifestations of the same adverse reaction can be fatal, e.g. mild airway obstruction is not life threatening but severe airway obstruction is.

*Hospitalization* includes any inpatient admission, any transfer within a hospital for the purpose of treatment (for example, transfer of a participant from a psychiatric unit to a general medical unit) and prolongation of admission. Prolongation of hospitalization is

defined as any extension of an inpatient hospitalization beyond the stay anticipated/ required in relation to the original reason for the initial admission, as determined by the investigator or treating physician.

Study coordinators will report any new SAEs to the PI, NYSPI IRB, DSMB and sponsor within 24 hours of first knowledge.

## 8.2 CLASSIFICATION OF AN ADVERSE EVENT

## 8.2.1 Severity of Event

- **Mild** Events require minimal or no treatment and do not interfere with the participant's daily activities.
- **Moderate** Events result in a low level of inconvenience or concern with the therapeutic measures. Moderate events may cause some interference with functioning.
- Severe Events interrupt a participant's usual daily activity and may require systemic drug therapy or other treatment. Severe events are usually potentially life-threatening or incapacitating.

## 8.2.2 Relationship to Study Medication and Surgical Procedure

The clinician's assessment of an AE's relationship to the study medication (i.e. OLANI) or the surgical procedure is part of the documentation process, but it is not a factor in determining what is or is not reported in the study. If there is any doubt as to whether a clinical observation is an AE, the event should be reported. All AEs must have their relationship to study agent assessed. In a clinical trial, the study product must always be suspect. To help assess, the following guidelines are used.

- **Definitely Related** There is clear evidence to suggest a causal relationship, and other possible contributing factors can be ruled out. The clinical event, including an abnormal laboratory test result, occurs in a plausible time relationship to drug administration and cannot be explained by concurrent disease or other drugs or chemicals. The response to withdrawal of the drug (dechallenge) should be clinically plausible. The event must be pharmacologically or phenomenologically definitive, with use of a satisfactory rechallenge procedure if necessary.
- **Probably Related** There is evidence to suggest a causal relationship, and the influence of other factors is unlikely. The clinical event, including an abnormal laboratory test result, occurs within a reasonable time after administration of the drug, is unlikely to be attributed to concurrent disease or other drugs or chemicals, and follows a clinically reasonable response on withdrawal (dechallenge). Rechallenge information is not required to fulfil this definition.
- **Possibly Related** There is some evidence to suggest a causal relationship (e.g., the event occurred within a reasonable time after administration of the trial medication). However, other factors may have contributed to the event (e.g., the participant's clinical condition, other concomitant events). Although an AE may rate only as "possibly related" soon after discovery, it can be flagged as requiring more information and later be upgraded to "probably related" or "definitely related," as appropriate.

- Unlikely to be related A clinical event, including an abnormal laboratory test result, whose temporal relationship to drug administration makes a causal relationship improbable (e.g., the event did not occur within a reasonable time after administration of the trial medication) and in which other drugs or chemicals or underlying disease provides plausible explanations (e.g., the participant's clinical condition, other concomitant treatments).
- Not Related The AE is completely independent of study drug administration, and/or evidence exists that the event is definitely related to another etiology. There must be an alternative, definitive etiology documented by the clinician.

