#### Table 2-5: Opiate Treatment SAE's by ICD10 description.

# 2.1.6.2.1 Inflammatory Reaction, Infection and Implant Removal

The highest number of ADR and SAE's were recorded as an 'Inflammatory reaction due to implants'. Patients are encouraged to see the doctor if a suspected inflammatory reaction is reported, with the standard treatment being oral treatment (prednisolone 50mg daily for 7 days). Due to the type of patients that are treated at AMPRF with the OLANI, not all patients will seek treatment early due to a number of factors that are usually related to their drug use lifestyle. Therefore, it can be common for patients to present to the AMPRF clinic after such time that a severe inflammatory response has occurred, which may result in the need for drainage of fluid that has built up. The fluid is sent for testing to ensure that the inflammation is not caused by a bacterial infection. In some cases, individual tablets of the OLANI will have been or are in the process of being excreted by the body. In such cases, the wound site will be cleaned and dressed to ensure that infection is minimized.

A breakdown of the number of treatment received by patients recorded as having an inflammatory response due to the OLANI is presented in Table 2-6.

Inflammatory Treatment	No. of Events	Total Events %	Unique Treatment Events*	Unique Treatment Events %
None	19	18.63%	16	21.92%
Oral Treatment	73	71.57%	47	64.38%
Fluid Drainage/Site cleaned	5	4.90%	5	6.85%
Non-Surgical Implant Removal	3	2.94%	3	4.11%
Surgical Removal	2	1.96%	2	2.74%
Grand Total	102	100.00%	73	100.00%

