#### 2.1.6.2.2 Conclusions

The ADR and SAE's data reported that the majority of events were due to inflammatory reactions, with about 11.26% (58 in 515) of treatments recording an inflammatory reaction. Of these, the majority could be classified as mild enough to require no further intervention or to be managed with standard oral treatment (prednisolone). Only 1.94% (10 in 515) of treatments could be classified as being more severe and requiring greater intervention of;

'fluid drainage/site cleaned' 0.97% (5 in 515), 'non-surgical removal' 0.58% (3 in 515) or surgical removal 0.38% (2 in 515).

The majority of inflammatory reports occur within the first 60 days of implantation with peak values around the 56 day mark. It should also be noted that this data represents reports of inflammatory reactions received by AMPRF either through proactive follow up questionnaires or patients reporting issues to the clinic. Natural attrition of follow up will occur over a period of 365 days and thus the reported inflammatory responses may be under reported in the latter period of the follow up.

After inflammatory reactions, the next most common ADR was related to withdrawal state - opiate 6.21% (32 in 515) and other associated drug withdrawal symptoms (Insomnia, Anxiety, Depression and Nausea) 7.96% (41 in 515).

Overall it can be concluded that the OLANI is safe and that the perception of efficacy amongst patients has outweighed any perceived inconvenience arising from the mild inflammatory reactions that have been observed. A method for treatment of inflammatory responses is effective with only a small amount of procedures requiring removal of an implant for an unresolved inflammatory response. It is also important to have good treatment plans in place to help patients post implantation to deal with the expected withdrawal symptoms and adjustment to a change in lifestyle from opiate dependence.

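### Section 8.2.2 makes a response to drug withdrawal a condition of 'probably related', which a surgical procedure can never meet and a once-placed implant can meet only if it is removed or expelled

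*Combined protocol and SAP*

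**What the plan says.** Section 8.2.2 covers an event's "relationship to the study medication (i.e. OLANI) or the surgical procedure is part of the documentation process". One set of five grades follows, with no separate definitions for the procedure.

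'Probably related' joins its conditions with 'and': reasonable timing, another cause being unlikely, and an event that "follows a clinically reasonable response on withdrawal (dechallenge". The next sentence relaxes one thing only: "Rechallenge information is not required to fulfil this definition". There is no 'where applicable' wording. 'Definitely related' also mentions dechallenge, but says only that the response should be plausible. 'Possibly related' has no dechallenge condition.

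The product is given once, as two units (6.1.5, 6.1.7), and dose modification is not applicable (6.1.8). Section 7.6.2 treats an inflammatory reaction with the implant left in place. Level 1 reads "Participants should be prescribed prednisone at 25 mg daily for the first 7 days". Levels 2 and 3 raise the steroid dose and then add local injection and drainage. Removal comes last, at Level 4: "In participants that do not respond adequately to the treatment regime, the implant(s) should be surgically removed". Expulsion is the other route by which exposure ends early; section 2.1.6.2.1 notes that in some cases "individual tablets of the OLANI will have been or are in the process of being excreted by the body".

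**The concern.** Dechallenge asks whether the event improved when the drug was stopped. That suits a daily tablet. It does not suit an incision that is already made, or a depot that stays in place while the reaction is treated.

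Hematoma and wound infection, which section 8.2.3.2 lists as common after implantation, have no withdrawal to observe. A local inflammatory reaction has one only if the implant comes out. Natural depletion does not fill the gap. Plasma naltrexone is expected to fall below 0.1 ng/mL by Day 540 (4.1), whereas inflammatory reports in the earlier review peaked around day 56 (2.1.6.2.2). Slow depletion might inform a long-lasting systemic effect, but not an early site reaction.

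What is at stake is the grade itself. The product's best-known reaction could sit at 'possibly related' because one condition could not be assessed and not because the evidence was weak. Section 10.4.4 collates adverse drug reactions without saying which grades count, so that collation could be affected too.

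**Working it through.** The plan states no figure on this point, so there is none to reproduce. The check has two parts: the wording, and how often dechallenge could be observed.

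**Wording, condition by condition**

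| Condition of 'probably related' | Implant-site reaction, implant kept | Procedure event (e.g. hematoma) |
|---|---|---|
| Reasonable timing | can be judged | can be judged |
| Other cause unlikely | can be judged | can be judged |
| Reasonable response on withdrawal | nothing withdrawn | cannot be withdrawn |
| Rechallenge | waived | waived |

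The third row fails for a reason unrelated to causation. Upgrading later from 'possibly', which the text allows, meets the same row again.

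**How often dechallenge could be observed**

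Inputs:
- 20 participants (5.3.1).
- Inflammatory reactions, section 2.1.6.2.2: "with about 11.26% (58 in 515) of treatments recording an inflammatory reaction".
- Removals among those reactions, same section: 3 non-surgical and 2 surgical, so 5 in 515.
- All removals in Tables 2-4 and 2-5: 5 for inflammatory response, 1 for another reason, 1 for infection, so 7 in 515.
- Section 2.1.5 gives a removal rate of 1.18% for unresolved inflammation in its own summary.
- Assumption: these rates carry over, with one treatment standing for one participant. They come from opioid-use patients with a mean of 2.49 implants (Table 2-2). Here the participants are healthy and receive 2 implants.

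Reactions with no removal to judge: (58 − 5)/58 = 53/58 = 91.4%.

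Expected reacting participants: 20 × 58/515 = 2.25. Chance of at least one: 1 − (1 − 58/515)^20 = 1 − 0.092 = 0.908.

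Chance of no removal in 20 participants, (1 − p)^20:

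| Removals counted | p | Expected in 20 | Chance of none |
|---|---|---|---|
| For inflammation, 2.1.6.2.2 (5/515) | 0.97% | 0.19 | 0.823 |
| For inflammation, 2.1.5 | 1.18% | 0.24 | 0.789 |
| All removals, Tables 2-4 and 2-5 (7/515) | 1.36% | 0.27 | 0.761 |

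Sampling error in the rate widens this. The Clopper-Pearson 95% interval for 5/515 is 0.32% to 2.25%, which gives a chance of none from about 94% down to 63%.

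On the 5/515 count, removals are a subset of reactions. The chance of at least one reacting participant and no removal is therefore 0.823 − 0.092 = 0.731.

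Expulsions are not counted separately in the earlier review. Treating all 5 drained or cleaned treatments as expulsions, in addition to the 5 removals, gives p = 10/515 and (1 − 10/515)^20 = 0.676.

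These figures show how rarely the condition could be tested. They are not the proportion of grades that would be wrong. Procedure events need no such calculation, because the condition is never available for them.

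**The case against.** The strongest reply is that little depends on the grade, and that a trained clinician would not be held back by a clause that cannot apply. Section 8.2.2 calls the definitions guidelines and says the study product must always be suspect. Section 8.3 leaves grading to those qualified to diagnose. Sections 8.2.3.2 and 8.2.3.4 list local inflammation as common after the procedure and from the polymer. This stands as a limit on the consequence. It does not repair the wording, and relying on assessors to ignore a written condition invites uneven grading between the SURC and Clinilabs clinics.

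A reader might infer that safety events would be missed or under-reported. The documents do not support that. Relationship does not decide what is reported (8.2.2), and all events are documented whatever their relationship (8.3). They go monthly to the sponsor and DSMB (8.4.1), and the DSMB reviews them all (8.6.3). SAEs are reported whether or not related (8.4.2.1). Wound-site and inflammatory rates are counted without reference to grade (10.4.4). No endpoint or stopping rule uses the grade.

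A reader might also infer that these events can never be graded above 'possibly'. That goes too far: 'definitely related' is less strictly tied to dechallenge, so a clear reaction along the implant track could be placed there.

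Nor is it shown that the adverse drug reaction collation would be distorted. If 'possibly' or above counts, moving an event from 'probably' to 'possibly' changes nothing. The effect exists only if the cutoff is 'probably' or above, and section 10.4.4 does not say.

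**Conclusion.** The definition of 'probably related' is wrong as written for this product and procedure, and the defect is minor. Applied literally, it excludes all procedure events and most implant-site reactions; in the sponsor's earlier series 53 of 58 inflammatory reactions had no removal to judge. It could understate attribution in the relatedness grades and, under one possible cutoff, in the adverse drug reaction collation. The harm stops there.

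For scale, about 2.3 of 20 participants would be expected to have an inflammatory reaction. The chance that no removal occurs is about 76% to 82%, depending on which removals are counted. Both figures rest on carrying rates over from opioid-use patients to healthy volunteers. The conclusion about the wording does not depend on them.

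**What to change.** In section 8.2.2, under both 'probably related' and 'definitely related', make the dechallenge condition apply only where the implant has been removed or expelled. Otherwise, grade on timing, location (implant track or incision) and exclusion of other causes. State that the procedure is graded on those same criteria, without dechallenge.

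Apply the revised wording going forward and at the final safety review, with the original grades kept and shown. Systematic regrading of past events is not needed: it would be open-label and exposed to hindsight, for little gain.

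The cost is a few lines of text and a note to assessors, with no extra visits or samples.
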